As part of the responsibilities assumed by participating in the study, the clinical investigators agree to maintain adequate case histories for the participants treated as part of the research under this protocol. The clinical investigators agree to maintain accurate CRFs (Annex 1) and source documentation as part of the case histories according to the instructions to complete CRF (Annex 2). The Sponsor will supply the CRFs. All CRFs should be completed legibly in black ink. The CRFs may not be completed in pencil.

All CRF information is to be filled in. If an item is not available or is not applicable, this fact should be indicated. Blank spaces should not be present unless otherwise directed. A correction should be made by striking through the incorrect entry with a single line and the corrected information should be entered adjacent to the deleted item. The correction must be initialed and dated by the person making the correction.

Each completed CRF must be reviewed, signed, and dated by the principal investigator and clinical monitor in a timely manner. The completed CRF will be checked by study monitors as soon as practical after completion. Scan copies of the CRF pages required to elaborate the interim report will be sent to the statistician responsible for the analysis of data during the study. At the end of the study

the site will send a scanned copy of all CRF to the Sponsor and will retain the originals at the site in the principal investigator's files.

Reports

Each site of Investigation will provide information about study progression to the Sponsor on a three months basis after the enrolment of first patient into the study. This information will be reported by the Sponsor in the form (Annex 5) provided by the Sponsor to the Principal Investigator/Site of Investigation.

In addition, each site of Investigation shall write, in English, an interim report (Annex 6) including all patients who have completed visit 5 (day 180), according to the ICH E3 guidance on structure and content of clinical study reports.

Each form must be filled with the following information:

- number of subjects visited at baseline (and/or reason for enrolment failure) (visit 1);
- number of subjects recruited (visit 1);
- number of subjects receiving the treatment (day 0);
- Average intracorneal concentration of riboflavin after dosing (day 0).
- Average intracorneal concentration of riboflavin at the end of treatment (day 0).
- Average Treatment Efficacy Index (day 0).
- Number of subjects completing visits after treatment.
- number of premature terminations/drop-outs.
- Average UDVA at each visit.
- Average CDVA at each visit.
- Average manifest refraction at each visit.
- Average ECD at each visit.
- Slit lamp biomicroscopy data at each visit.
- Interim analysis of primary outcome measure at 6-months.
- Adverse events (number and type).
- Missing data.
- Other information (if any).

A final report (Annex 7) shall be elaborated in written (English) according the ICH E3 guidance on structure and content of clinical study reports and sent to the Sponsor for approval. The Final Report will compile all the data collected from all the participants during the entire duration of the study (from screening to the end of follow-up, including AE (if any), discussion of statistical analysis as well as interpretation of the results. This report will be sent to the Sponsor within 2 weeks from the final

monitoring visit performed by the Sponsor to confirm the correctness and completeness of the data collected and database lock. In the Final Report, a clear conclusion on the following points must be provided:

- Assessment of primary outcome measure at 12 months (day 360), such as:
 - Validation of the combined use of the theranostic imaging biomarkers. True positives, false positives, true negatives and false negatives were evaluated in order to determine the ability of the theranostic imaging biomarkers, including both the *riboflavin score* and *theranostic score*, to predict the propensity of CXL treatment in flattening the K_{max} value (D) by more than 0.1 D at 12 months postoperatively.
- Assessment of all secondary outcome measures, such as:
 - Change of Maximum Keratometry assessed by corneal topography at 12-months.
 - Change of Endothelial Cell Density assessed by specular microscopy at 12-months.
- Assessment of the additional exploratory outcome measures, such as:
 - Change of Corrected Distance Visual Acuity (CDVA) assessed by ETDRS at 12-months.
 - Change of Uncorrected Distance Visual Acuity (UDVA) assessed by ETDRS at 12-months.
 - Change of Manifest Refraction assessed by ETDRS at 12-months.
 - Change of secondary outcome measures at 12-months in either stratification group.

Study Reporting Requirements

By participating in this study, the Principal Investigator/Site of Investigation agree to provide the Sponsor with the adequate study reports, as defined in the “Reports” section above.

The Principal Investigator/Site of Investigation agree to submit reports of AEs and SAEs according to the timeline and method outlined in the protocol. In addition, the Principal Investigator/Site of Investigation agree to submit a report to the IEC as appropriate.

Monitoring of the Study

The Site of Investigation has the obligation to follow the study closely and to support the by Sponsor in monitoring the study. In doing so, the Principal Investigator/Site of Investigation will assist the Sponsor to visit the study facility as defined in the monitoring plan, in addition to maintaining necessary contact through telephone, email, and letter. The Sponsor will maintain current personal knowledge of the study through observation, review of study records and source documentation, and discussion of the conduct of the study with the principal investigator or staff. All aspects of the study

must be carefully monitored for compliance with applicable government regulation with respect to current GCP and current standard operating procedures.

Monitoring Plan

On-site monitoring will be performed by the Sponsor at the Site of Investigation before commencing the study and at the end of the study (after visit 6, i.e., 360 days after all participants have been treated). On-site monitoring will be carried out to verify that:

- the Principal Investigator receives the current Investigator's Brochure, all documents, and all trial supplies needed to conduct the trial properly and to comply with the applicable regulatory requirement(s).
- the Principal Investigator and Study Staff have adequate experience and have been adequately informed and trained to carry the study.
- the Site of Investigation has adequate resources to carry the study.
- the investigators follows the approved protocol and all approved amendment(s).
- written informed consent was obtained before each subject's participation in the trial.
- the storage of the RitSight™ are acceptable, and that supplies are sufficient throughout the trial.
- the disposition of unused investigational product(s) at the trial sites complies with applicable regulatory requirement(s) and is in accordance with the sponsor.
- the RitSight™ is supplied only to subjects who are eligible to receive it and at the protocol specified doses.
- the CRF entries and other operating documents are filled with accuracy and completeness by Investigators.
- If CRFs have any entry error, omission, or illegibility, informing the investigator of it. The Sponsor shall ensure that appropriate corrections, additions, or deletions are made, dated, explained (if necessary), and initialed by the principal investigator.
- all adverse events are appropriately reported within the time periods required by GCP, the protocol, the IEC, the Sponsor, and the applicable regulatory requirement(s).
- if deviations from the protocol occur, communicating the applicable regulatory requirements to the investigator and taking appropriate action designed to prevent recurrence of the detected deviations.

Centralized monitoring will be performed by the Sponsor to review interim and final reports provided by the Principal Investigation/Site of Investigation. Review will include analyses of study data, including the following actions:

- to identify missing data, inconsistent data, data outliers, unexpected lack of variability and protocol deviations.
- to evaluate for systematic or significant errors in data collection and reporting at a site or across sites; or potential data manipulation or data integrity problems.
- to perform statistical analysis of study data.

Inspection of Records

The Principal Investigator/Site of Investigation will permit, at any working day, trial-related monitoring, audits, IEC review, and regulatory inspection(s) by providing direct access to all study records. In the event of an audit, the Principal Investigator/Site of Investigation agrees to allow the Sponsor, representatives of the sponsor, the Regulatory authorities to access to all study records.

The Principal Investigator/Site of Investigation should promptly notify the Sponsor of any audits scheduled by any regulatory authorities and promptly forward copies of any audit reports received to the sponsor.

Study Record Retention

Essential documents should be retained until at least 5 years after the last approval of a marketing application in an ICH region and until there are no pending or contemplated marketing applications in an ICH region or at least 3 years have elapsed since the formal discontinuation of clinical development of the investigational product. These documents should be retained for a longer period, however, if required by the applicable regulatory requirements or by an agreement with the Sponsor. It is the responsibility of the Sponsor to inform the Principal Investigator/Site of Investigation as to when these documents no longer need to be retained.

Quality Assurance

The Sponsor is responsible for implementing and maintaining quality assurance and quality control systems to ensure that the study is conducted and data are generated, documented and reported in compliance with the protocol, GCP and the applicable regulatory requirements. The Sponsor ensures that case report forms, and other operational documents are clear, concise, and consistent. The Sponsor shall make sure that each C4V CHROMO4VIS™ system and each batch of the RitSight™ eye drop meets the requirements and that is properly delivered to the Site of Investigation. The Principal Investigator/Site of Investigation ensures the accuracy, completeness, legibility, and timeliness of the data reported to the Sponsor in the CRFs and in all required reports. The Principal Investigator/Site of Investigation ensures that there is adequate training for all staff participating in

the conduct of the study, and that they are aware of regulatory requirements and acceptable standards for the conduct of clinical trials and the protection of human subjects.

The Sponsor ensures to monitor that all operating documents are using standard terminology and to provide systematic safeguard to ensure adherence to study protocol by the Principal Investigator/Site of Investigation.

Confidentiality

All evaluation forms, reports, and other records will be identified in a manner designed to maintain participant confidentiality. All records will be kept in a secure storage area with limited access. Clinical information will not be released without the written permission of the participant [or the participant's legal guardian], except as necessary for monitoring and auditing by the sponsor, its designee, the regulatory authorities, or the IEC.

The Principal Investigator/Site of Investigation shall not disclose or use for any purpose other than performance of the study, any data, record, or other unpublished, confidential information disclosed to those individuals for the purpose of the study. Prior written agreement from the Sponsor must be obtained for the disclosure of any said confidential information to other parties.

Personal data protection

The study adheres to the General Data Protection Regulation (GDPR). The rights of each participant to the study to physical and mental integrity, to privacy and to the protection of the data ("personal data") concerning him/her in accordance with data protection laws, are safeguarded. Personal data include any information relating to an identified or identifiable natural person ('data subject'); an identifiable person is one who can be identified, directly or indirectly, in particular by reference to an identification number or to one or more factors specific to his physical, physiological, mental, economic, cultural or social identity. The Sponsor monitors whether the Principal Investigator/Site of Investigation performs the study in conformity with the protocol and safeguard personal data. In this study, data records are key-coded data and thus any other person cannot de-code the data easily. The Sponsor and the Principal Investigator/Site of Investigation will take appropriate actions to safeguard personal data of the study. The data controller is the legal representative of the Sponsor; the data processor is the Principal Investigator.

Modification of the Protocol

Any changes in this research activity, except those necessary to remove an apparent, immediate hazard to the participant, must be reviewed and approved by the Sponsor. Amendments to the

protocol must be submitted in writing to the IEC for approval prior to participants being enrolled into an amended protocol.

Protocol Violations and Deviations

The Principal Investigator/Site of Investigation must document and explain in the participant's source documentation any deviation from the approved protocol. The Principal Investigator/Site of Investigation may implement a deviation from, or a change of, the protocol to eliminate an immediate hazard to trial participants without prior IEC approval. As soon as possible after such an occurrence, the implemented deviation or change, the reasons for it, and any proposed protocol amendment(s) should be submitted to the IEC for review and approval, to the sponsor for agreement, and to the regulatory authorities, if required.

A deviation from the protocol is an unintended and/or unanticipated departure from the procedures and/or processes approved by the Sponsor and the IEC and agreed to by the Principal Investigator/Site of Investigation. Deviations usually have an impact on individual participants or a small group of participants and do not involve inclusion/exclusion or primary endpoint criteria. A protocol violation occurs when there is nonadherence to the protocol that results in a significant, additional risk to the participant, when the participant or Principal Investigator/Site of Investigation has failed to adhere to significant protocol requirements (inclusion/exclusion criteria) and the participant was enrolled without prior sponsor approval, or when there is nonadherence to authorities regulations.

The Sponsor will document protocol violations and deviations throughout the course of monitoring visits. The Sponsor will notify the principal investigator during a visit and/or in writing of all violations and deviations. The IEC should be notified of all protocol violations and deviations in a timely manner.

List of major deviations/violation

- Patient not met inclusion criteria
- Patient not met exclusion criteria
- Not obtained signed consent form from patient
- Corneal topography not done at visit 1 (baseline)
- Corneal topography not done at visit 6 (day 360)
- Corneal cross-linking treatment not completed

Financial Disclosure and Obligations

The clinical investigators are required to provide financial disclosure information to allow the Sponsor to submit the complete and accurate certification or disclosure statements to regulatory authorities. In addition, the principal investigator or investigators must provide to the Sponsor a commitment to promptly update this information if any relevant changes occur during the course of the investigation. The clinical investigators are required to provide an updated curriculum vitae (CV).

The Sponsor is not financially responsible for further testing/treatment of any medical condition, which may be detected during the screening process. In addition, in the absence of specific arrangements, the Sponsor is not financially responsible for further treatment of the participant's disease.

Study Conduct

The Principal Investigator/Site of Investigation agree that the study will be conducted according to the principles of the ICH E6 Guideline for Good Clinical Practice and the principles of the World Medical Association Declaration of Helsinki. The Principal Investigator/Site of Investigation will conduct all aspects of this study in accordance with all national, state, and local laws or regulations.

Recruitment strategies

The screening and the recruitment processes will respect the dignity and autonomy of the potential participants by avoiding any potential undue influence and by protecting both the privacy of the individual and the confidentiality of any information obtained for recruitment and/or screening purposes.

In preparing recruitment materials the Principal Investigator/Site of Investigation shall consider the purpose of the research and the setting in which the research will be conducted. The following methods of recruiting subjects will be considered acceptable:

- Direct recruitment of potential study participants

Examples of this strategy are physicians talking with their own or clinic patients about the study, contact between the study team and potential subjects in person, on the phone or on the internet. With this method considerable care will have to be taken so that the person contacted does not feel pressured to participate.

- Referrals

Referrals may be from non-investigator healthcare providers, participants referring other participants.

- Advertisements, flyers, information sheets, notices, internet postings and/or media can be used to recruit subjects.

Prospective participants who respond to these will contact directly the Site of Investigation.

Recruitment materials can contain the following Information:

1. The name of the institution(s);
2. The name of the Principal Investigator(s) and Sponsor, and the name of a contact person with a telephone number and email address to call and write for information about the study;
3. The purpose of the research and, in summary form, the eligibility criteria that will be used to admit subjects into the study;
4. The location of the research and time commitment, if appropriate.

The Promoter and Sponsor can prepare advertisements, information sheets, notices, internet postings and/or media but cannot directly contact prospective subjects (see Annex 12). Per-participant incentive payments or referral fees, whether paid for each referral or each enrollment, are not allowed.

Publications

Clinical data are the property of the Sponsor and cannot be published without prior authorization from the Sponsor, but data and publication thereof will not be unduly withheld.

The data of the study may be considered for reporting at a scientific meeting or for publication(s) in a scientific journal. In these cases, the Sponsor will be responsible for these activities and will decide who will eventually present study outcomes at a scientific meeting, if and how the manuscript(s) is written and edited, the number and order of authors, the scientific journal(s) to which it/they will be submitted, and other related issues. The Sponsor has final approval authority over all such issues.

Study Termination

The Sponsor may prematurely terminate the study in case of major violations, which may prevent the safety of the subjects or future evaluation of the study results. In addition, the Sponsor, may prematurely terminate the study, in its sole discretion and for any reason whatsoever associated with changes in its commercial or clinical strategy.

In such an occurrence the Sponsor shall give at least thirty (30) calendar days' written notice of termination to the study centre. All the effort will be made to perform a final visit to all the subjects still in the study aiming to confirm their wellbeing.

References

(in alphabetical order)

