Synopsis on disposition of participants

Sample size

By expecting a response rate of 50% of cases that will reach the threshold of -1.05 D of the K_{max} value, a sample size of 42 patients achieves 91% power to detect a difference of 0,25 between the area under the ROC curve (AUC) under the null hypothesis of 0,60 and an AUC under the alternative hypothesis of 0,85 using a two-sided z-test at a significance level of 0,05000. The data are continuous responses. Considering a $\leq 20\%$ drop-out rate (determined from systematic literature review on controlled and open clinical studies on standard and epithelium-on CXL procedures), a number of 50 participants (25 per treatment protocol) is allowed to be enrolled in the study.

Details on the methodology and process used to define the sample size of this clinical trial are described in Appendix 1 – Methodology for sample size calculation.

Statistical methodology

Descriptive statistics will be used to summarize the data: numerical variables will be summarized as mean and standard deviation or median and interquartile range, respectively, according to the distribution of the data; categorical variables will be represented as frequencies and proportions. Student's t-test or Wilcoxon test will be applied to compare continuous variables, while Fisher's exact test or Chi-Squared test will be used to analyze categorical variables. Bonferroni correction is applied to analysis of exploratory outcome measures of stratification groups. For all reported AEs, the data can be presented with events listed in order of decreasing frequency.

The optimal cut-off values in predicting the propensity of CXL treatment to flatten the Kmax value at 12-months was determined based upon the results of preclinical studies (data not disclosed to investigators to avoiding methodological study bias) and can be optimized with the Youden index. The accuracy and precision (95% CI) of the combined use of the theranostic imaging biomarkers to predict CXL treatment outcome will be determined by calculating the proportion of correctly classified eyes and the positive predictive value (PPV) respectively. The miss rate, which is the probability that a true positive is missed by the theranostic methodology, will be determined by calculating the false negative rate (FNR).

Statistical significance will be set at 0.05. All the analysis will be performed using the statistical software R (latest version available).

Population to be analysed

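### The day-180 site report calls for an interim analysis of the primary outcome that the statistical section never describes, while the biomarker cut-offs are still open

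*Combined protocol and SAP*

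**What the plan says.** Under Reports, "each site of Investigation shall write, in English, an interim report (Annex 6) including all patients who have completed visit 5 (day 180"). The required contents include average riboflavin concentrations, the average Treatment Efficacy Index and "Interim analysis of primary outcome measure at 6-months".

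Under Primary outcome measure, the primary outcome is the two-by-two classification of eyes by the riboflavin and theranostic scores against Kmax flattening of more than 0.1 D, at 12 months. Success means accuracy and PPV of at least 85% in the per-protocol population.

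On the cut-offs, Statistical methodology says that they come from preclinical studies ("data not disclosed to investigators to avoiding methodological study bias) and can be optimized with the Youden index"). The Statistical Methods text of the Synopsis says that the cut-off is to be chosen by the Youden index.

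On who sees what:
- The case report form text just before Reports says that the pages needed for the interim report "will be sent to the statistician responsible for the analysis of data during the study".
- The Monitoring Plan says "Centralized monitoring will be performed by the Sponsor to review interim and final reports", and lists statistical analysis of study data among the sponsor's actions.
- The investigator records Kmax at every visit (Secondary outcome measures).
- The sponsor and principal investigators agree the analysis populations after the last visit and before database lock (Population to be analysed).

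Statistical Considerations and Data Analysis does not mention an interim analysis.

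**The concern.** A validation study is convincing when the rule under test is fixed in advance and the reference standard is recorded without knowledge of how the rule is doing. Here an analysis of the primary outcome is scheduled halfway through follow-up, and the site writes it up. Three things are still open at that point: the day-360 Kmax readings, the membership of the per-protocol population and, on the current wording, the cut-offs. The plan itself treats investigator knowledge of the basis of the cut-offs as a source of bias, yet its reporting form can return a performance result to the same people. At stake is how far the final accuracy and PPV can be read as independent validation.

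**Working it through.** **1. The plan's own figure.** Inputs (Sample size section): N = 42, 50% responders (21 and 21), AUC 0.60 against 0.85, two-sided alpha 0.05. Hanley-McNeil variance: [A(1−A) + 20(Q1−A²) + 20(Q2−A²)]/(21×21), with Q1 = A/(2−A) and Q2 = 2A²/(1+A).
- A = 0.60: (0.240 + 1.371 + 1.800)/441 = 0.00774, SE 0.0880.
- A = 0.85: (0.1275 + 0.3326 + 1.1716)/441 = 0.00370, SE 0.0608.
- Power = Φ[(0.25 − 1.96×0.0880)/0.0608] = Φ(1.28) = 89.9%, against 91% stated. Other variance formulas give 88.3% and 92.7%.

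The figure reproduces. All of the alpha is used in one test, with none set aside for an interim.

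**2. What the interim item needs.** A two-by-two table needs a cut-off. Either the site is given one, or the site derives one from its own eyes, or the statistician classifies the eyes and returns counts. The documents do not say which. In all three cases the site report ends up with a result on how the scores perform.

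**3. What is still to come at that time.** Enrolment runs for four months from local approval, about 122 days. If treatment follows enrolment promptly, a site's last visit 5 falls by about day 122 + 180 + 14 = 316. The earliest visit 6 is day 360 minus 21 working days (about 30 calendar days), so about day 330. A report written when the last patient completes visit 5 would therefore precede every day-360 reading at that site. The documents do not date the report more closely. Treatment would be complete by then, so the bias routes are measurement, population decisions and choice of cut-off, not allocation or treatment.

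**4. Size of the open cut-off.** Simulation: one equal-variance binormal score, 6,000 runs per setting, 50% responders. The fixed cut-off is at the true midpoint, where expected accuracy is Φ(d/2) with d = √2·Φ⁻¹(AUC). For AUC 0.85, d = 1.466 and Φ(0.733) = 76.8%, which agrees with the simulated value.

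| True AUC | Eyes | Mean accuracy, fixed | Mean accuracy, Youden on same eyes | Accuracy and PPV both ≥85%: fixed | Same: Youden |
|---|---|---|---|---|---|
| 0.60 | 42 | 57.2% | 64.2% | 0% | 0% |
| 0.75 | 42 | 68.3% | 73.7% | 0.7% | 1.9% |
| 0.85 | 42 | 76.9% | 81.3% | 8.3% | 18.1% |
| 0.85 | 14 | 76.7% | 84.6% | 28.4% | 48.3% |

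At 42 eyes the gain in apparent accuracy is 4.4 to 7.0 points. The 14-eye row is 42/3. It assumes equal sites, although enrolment is competitive.

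**5. Month 6 against month 12.** Share of eyes flattening by more than 0.1 D = Φ[(−0.1 − mean)/SD], taking the Appendix 1 means and SDs as normal (an assumption):
- Pooled, 6,995 cases: month 6 Φ(0.69/0.75) = 82%; month 12 Φ(0.95/0.80) = 88%.
- Standard protocol, 354 cases: Φ(0.79/0.60) = 91%; Φ(1.31/1.71) = 78%.
- Transepithelial, 91 cases: Φ(0.42/1.20) = 64%; Φ(0.22/1.55) = 56%.

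The two time points are different endpoints. The direction of the difference depends on the source. In the standard-protocol subset the mean improves (−0.89 to −1.41 D), so the fall comes from the larger SD at month 12.

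**The case against.** The strongest reply is that the item may not be the classification at all. The interim list has no separate Kmax entry, the Synopsis states the objective in terms of mean Kmax change, Appendix 1 gives 6-month Kmax benchmarks, and the two-by-two definition is tied to 12 months. The item could simply mean Kmax change at 6 months. Annex 6, which might settle it, is not among the documents. This stands, and it makes the point conditional. The firm defect is an undefined item.

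Five stronger readings are tempting, and the documents do not support them:
- That a masking of the trial's score-outcome relation is broken. Only the preclinical basis of the cut-offs is withheld. Operators see each eye's index at treatment, and investigators record Kmax at each visit. The interim would turn values they already hold into a performance verdict.
- That sites must be told the cut-offs. The statistician receives the pages and could return counts alone. However, no firewall is described, and the counts are themselves a performance result.
- That the type I error is inflated. Two looks at |z| > 1.96 would give 7.0% to 9.1% for assumed correlations of 0.9 to 0.5, but the plan states no interim test, success claim or stopping rule.
- That month 6 flatters the device. The pooled figures point the other way.
- That the sponsor may stop on the interim result. Study Termination says that it "may prematurely terminate the study, in its sole discretion and for any reason whatsoever", but the sentence goes on to tie those reasons to changes in commercial or clinical strategy. No link to interim results is stated.

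Two further limits are fair. Kmax is an instrument reading, and the per-protocol definition is largely rule-based (visit counts and a list of major deviations), so investigators' room for influence is limited. Tuning of the cut-off is also possible without the interim, because the sponsor analyses study data anyway. Deleting the report line alone would not close that route.

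**Conclusion.** The point holds in a limited form. The plan requires a site-written 6-month analysis that its statistical section leaves undefined. Read as the primary outcome is defined, that analysis gives a performance result to the people who go on to record the reference standard and help agree the per-protocol population, and to the sponsor, before the cut-offs are fixed. This works against the plan's own reason for withholding the preclinical data.

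The bias from the interim itself cannot be calculated from the documents. The 4.4 to 7.0 point gain in apparent accuracy is the price of leaving the cut-off open, with or without an interim. It rests on one binormal score and 50% responders. The 50% figure belongs to the −1.05 D threshold in the sample size, not to the 0.1 D endpoint. The plan combines two scores, which was not simulated.

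This is an inexpensive improvement, not a fatal flaw.

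**What to change.** 1. Sign and date the cut-offs for both scores, and the rule that combines them, before any outcome data are analysed. Reconcile the Synopsis with Statistical methodology on this. This step closes the tuning route.
2. Remove the primary-outcome item from the site interim report and Annex 6, leaving enrolment, safety and data quality. Deleting the average Treatment Efficacy Index as well would gain little: a site mean shows no score-outcome relation, and operators already see every value.
3. If an interim look is wanted, the statistician alone should run it after the cut-offs are locked. Nothing should go to the sites until the last day-360 topography is done and the populations are fixed. The statistical section should define the 6-month quantity and say that it carries no success or stopping decision.
4. Reconcile the withholding of preclinical cut-off data with the statement under Risk Assessment and Management that sites have full access to the relevant preclinical work.

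The cost is a wording change to the protocol and Annex 6. Sites and sponsor lose an early look at performance. No safety information is lost.
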